ComPACT	Comprehensive Assessment of Acceptance and Commitment Therapy Processes
CRF	Case Report Form
CYP-ID	Children and Young People with an Intellectual/Learning Disability
DASS-21	Depression Anxiety and Stress Scale (21 item version)
GCP	Good Clinical Practice
ICH	International Conference on Harmonisation
ID	Intellectual Disability
PI	Principal Investigator
PBS	Positive Behaviour Support
QA	Quality Assurance
RCT	Randomised Controlled Trial
REC	Research Ethics Committee
SAE	Serious Adverse Event
SAR	Serious Adverse Reaction
SOP	Standard Operating Procedure
SUSAR	Suspected Unexpected Serious Adverse Reaction
TAU	Treatment As Usual
WEM	Workshop Evaluation Measure

1 INTRODUCTION

1.1 BACKGROUND

The Scottish Mental Health Strategy 2017-2027 (Scottish Government, 2017) emphasises the need to improve the supports surrounding children, including focusing upon the quality of parent-child relationships, the school environment and provision of tier one and two mental health services. The strategy identifies that children and young people with intellectual disability (CYP-ID) and autism spectrum disorder (ASD) have the highest rates of mental health difficulties. Furthermore, up to 60% of CYP-ID present with challenging behaviour (CB; Adams & Allen, 2001)

Challenging Behaviour

CB is defined as “behaviour that puts the individual or others at risk and/or could lead to the limitation of an individual’s access to their community” (British Psychological Society, 2018, p. 2). CBs, which can include aggression, self-injury and disruptive behaviours, have a significant impact on the child, their family and the services that support them (Fox et al., 2002). Positive behaviour support (PBS) is widely accepted to be the best practice model to support CB (British Psychological Society, 2018). PBS aims to improve quality of life of individuals with intellectual disability in a values-based and person-centred manner (see Carr et al., 2002 for a review).

Stress and Distress in Parents and Teachers

However, PBS can be very demanding for the systems around young people to implement, especially in a consistent manner. Parents of children with an ID have been shown to have significantly higher rates of parenting stress and mental health difficulties (Hassall et al., 2005; Olsson & Hwaang, 2001), it is key that they are also provided with appropriate support so that they can implement the intensive PBS plans and have close, high-quality relationships with their children.

Furthermore, teaching is amongst the occupations with the lowest levels of job satisfaction and highest stress levels (Johnson et al., 2005). Indeed, this appears to be an even greater issue within schools for CYP-ID, where a relationship between child behaviour difficulties and emotional exhaustion has been identified (Hastings & Brown, 2002). Considering that all education staff “have a responsibility to support the mental, emotional, social and physical wellbeing of pupils” (Scottish Government, 2017, p.13), they also require appropriate support and intervention to be able to do so, in the context of the high levels of stress they experience.

Acceptance and Mindfulness-based Interventions

Positively, there is a developing evidence base for the effectiveness of acceptance and mindfulness-based interventions for reducing the psychological stress and distress experienced by support staff, parents and teachers. Acceptance and Commitment Therapy (ACT), a third-wave of cognitive and behavioural therapies, was developed by Hayes, Strosahl and Wilson (1999). ACT supports individuals to live life based on their values, to willingly experience difficult emotions and to be able to step back and ‘defuse’ from difficult thoughts, with the aim to increase psychological flexibility (Blackledge & Hayes, 2006). Psychological flexibility is defined as “the capacity to persist or to change behaviour in a way that includes conscious and open contact with thoughts and feelings, appreciates what the situation affords, and serves one’s goals and values” (McCracken & Morley, 2014, p.225). Mindfulness is a core process within ACT but is also practiced within mindfulness-based

cognitive therapy and mindfulness-based stress reduction, which both also have well-developed evidence bases (see Gu et al., 2015).

ACT has often been described as a particularly appropriate intervention for parents and staff working with CYP-ID, given that their appraisal of the difficulties they face may often be realistic and thus perhaps less amenable to traditional cognitive behavioural strategies (Blackledge & Hayes, 2006). Recent meta-analyses of ACT have identified a developing evidence base for many psychological presentations, where ACT is superior to treatment as usual (TAU) and equivalent to cognitive-behavioural therapy (see A-Tjak et al., 2015; Öst, 2014).

Support Staff

The evidence base for acceptance and mindfulness-based interventions for supporting systems around people with ID is most well-developed for support staff of adults with ID. A recent systematic review concluded that there is sufficient evidence for short term benefits for mindfulness-based interventions with paid support staff (Ó Donnchadha, 2018). However, the review identified that only three of the eight studies were of adequate quality, with others notably limited due to small sample sizes, and lack of appropriate follow-up and appropriate controls. Of note within the high-quality studies is an ACT group workshop intervention for support staff, with a randomised waitlist control design and six-week follow-up (McConachie et al., 2014). The results demonstrated a significant reduction in psychological distress in the ACT condition, with an increased effect for those with higher levels of distress at baseline. This study highlights the potential utility for this 'dosage' of ACT within this population.

Teachers

Within a teacher population, a relatively small RCT of an ACT workshop for early years education staff working with CYP-ID demonstrated improvements in teacher's self-reported self-efficacy, willingness to experience emotion and mindfulness, although was not reported to improve ratings of depression (Biglan et al., 2013). While the study did not provide an active control with which to compare the ACT intervention, it provides preliminary evidence for the effectiveness and acceptability of ACT workshops with teachers working in special education environments.

Parents

Considering the provision of ACT to parents with CYP-ID, Blackledge and Hayes (2006) conducted an uncontrolled small study of a two-day ACT group workshop for parents of children with autism. The results identified significant improvements in depression and psychological distress both after the group and at a three-month follow-up. However, the changes could not be reliably attributed to the intervention in the absence of appropriate controls. Furthermore, Reid and colleagues (2016) qualitatively evaluated an ACT group for parents of children and young people with severe ID and challenging behaviour. The group was delivered in a workshop format with two days of four-hour groups. Themes identified from interviews suggested that participants had felt that they were at a "crunch point" (Reid et al., 2016, p.9) before the intervention, that they had liked the focus on their own wellbeing and the group format. The authors acknowledged that they were unsure about the applicability of the group to parents of children with less severe ID, and highlighted that quantitative analysis was needed to measure changes in parents' distress. Interestingly, this ACT intervention was delivered in the context of a service where PBS was also being provided. While the ACT intervention was not evaluated in this context, this is suggestive of the close link between the two interventions and how they may each increase the others effectiveness.

The role for Positive Behavioural Support

Therefore, there is an argument for strengthening the ties between ACT and PBS when providing interventions to families. Dunlap and Fox (2007) have argued that a key feature of PBS plans is the development of a parent-professional partnership, where parents function as collaborators in the development and implementation of the plan. This shift from the 'expert model' is of such significance because it is largely parents and teachers that implement PBS plans, and thus it is important that they have a high level of perceived self-efficacy for managing challenging behaviour. Where parents and teachers have been involved in the PBS process and their development of self-efficacy for managing challenging behavior has been supported, the intervention is more likely to socially valid and implemented (Dunlap & Fox, 2007; Dunlap et al., 2001; Gore et al., 2013). However, research suggests that parents describe rarely experiencing partnership with professionals (Wodehouse & McGill, 2009). It is proposed that where professionals are the only ones to hold knowledge of PBS, this power imbalance is likely to remain (Proctor, 2008). Moreover, the recent NICE guidelines for the management of CB advises that families should be provided with "skills training and emotional support, or information about these, to help them take part in and support interventions for the person with a learning disability and behaviour that challenges" (2015, p.60).

Interestingly, some work has begun on including PBS instruction in third-wave interventions within this population. Singh and colleagues (2014) completed a multiple baseline design study with three mothers of children with ASD who were displaying high levels of challenging behaviours. The mothers all previously had PBS plans that they had stopped implementing due to the associated stress this had caused. On completion of an eight-week mindfulness-based PBS programme (MBPBS), the results identified statistically significant reductions in maternal stress and significant reductions in recorded incidents of challenging behaviour. This work was extended with a RCT with support staff of adults with ID, comparing MBPBS with TAU, applied behavioural analysis training (Singh et al., 2016). The findings identified that the MBPBS condition was significantly more effective than TAU in reducing staff stress, and reducing challenging behaviours, emergency medications and staff turnover.

Current Study

Considering the currently available research, it appears that there is a developing evidence base for ACT and mindfulness-based interventions for parents, teachers and support staff, and for mindfulness-based PBS for parents and support staff. However, it appears that there is yet to be a quantitatively evaluated parent ACT workshop or combined ACT and PBS-based intervention. ACT and PBS are theoretically paired well together, in the context of their values focus and emphasis on increasing quality of life in a meaningful way. Given that parents and teachers both appear in need of access to these psychological interventions to support them in their distress and in their implementation of PBS, in this study, parents and teachers of CYP-ID will participate in a mixed methods study evaluating the effectiveness and mechanisms of an ACT and PBS based group workshop. The workshop format should fit well within tier one and two mental health services and provide a sustainable way to systemically improving the wellbeing of children and young people with IDs and the caregivers around them.

Quantitative Research Questions

- Is an ACT and PBS based group workshop ("the intervention") effective in reducing the psychological distress experienced by parents and teachers who work with children with IDs?
- Is the intervention effective in increasing parents and education staff self-efficacy in managing children's challenging behaviour?
- Is the intervention effective in reducing education staff's self-reported experience of burnout?
- Is there a significant change in the parents and education staff Acceptance and Commitment Therapy processes?

Qualitative Research Question

- In which contexts and through which mechanisms does the group work to achieve these outcomes?

Study Hypotheses

- The intervention will be effective in significantly reducing the psychological distress self-reported by parents and teachers who work with children with IDs.
- The intervention will be effective in significantly increasing parents and education staff self-reported self-efficacy in managing children's challenging behaviour.
- The intervention will be effective in significantly reducing education staff's self-reported experience of burnout.

Study Risks and Benefits

The study will aim to ensure that all participants have capacity to give informed consent and that they are not pressured into participating. Confidentiality will be maintained where appropriate, with safeguarding measures in place to safely manage any disclosures that occur during the study. It is possible that by participating in the group, focus group or completing the study questionnaires, that participants may experience some distress. This will be safely managed by signposting participants and communicating with their GP as appropriate. However, participants also may benefit from the therapeutic group and consequently experience a reduction in psychological distress and a possible improvement in their child's wellbeing. Participants may also derive some satisfaction from their involvement in the research.

2 STUDY OBJECTIVES

2.1 OBJECTIVES

2.1.1 Primary Objective

- To evaluate whether an ACT and PBS based workshop ("the intervention") is effective in reducing the psychological distress experienced by parents and education staff who work with children with Intellectual Disability.

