2.1.2 Secondary Objectives

- To evaluate whether the intervention is effective in increasing education staff and parents' self-efficacy in managing children's challenging behaviour.
- To evaluate whether the intervention is effective in reducing the self-reported burnout of education staff.
- To examine in which contexts and through which mechanisms the group works to achieve these outcomes.

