2.2.2 Secondary Endpoints

The secondary outcome measures are as follows:

- The Challenging Behaviour Self-Efficacy Scale (CBSES)

- Copenhagen Burnout Inventory (CBI) (Education staff only)
- Comprehensive Assessment of Acceptance and Commitment Therapy Processes (ComPACT)
- Workshop Evaluation Measure (WEM)

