3 STUDY DESIGN

- The study has a mixed-methods design and draws upon a realist evaluation framework. The mixed methods approach allows the utilisation both quantitative and qualitative approaches to gain a greater level of detail than either one methodology would allow for individually, and for the results to support a firmer conclusion if the differing methodologies corroborate each other. The realist evaluation approach is a relatively new framework for research and aims to answer “what works for whom in what circumstances” (Pawson & Manzano-Santaella, 2012, p.177). Realist evaluation tends to critique randomised controlled trials and other evaluations as overly focused on aggregate outcomes which evaluate interventions in a binary way as successful or unsuccessful. Realist evaluation suggests that it might be more helpful to consider the context in which the intervention has been implemented and how this has interacted with mechanisms to produce the outcomes observed. This framework has been chosen to guide the mixed-methods approach in this study as it is particularly relevant given the complexity of delivering psychological interventions in this population, and the many factors that may influence their effectiveness.
- Participants may be involved in the study for a period of approximately six months, due to the expectation that they may need to wait for a group appropriate to them to begin. Participants will be actively involved in the group for nine weeks, with three weeks of group sessions, and a focus group six weeks after this.
- The study will take place in NHS Lothian buildings, schools or in community facilities.

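### The objectives ask whether the workshop is effective, but a design with no described comparator can show only before-to-after change, and no result is named as the test of that change

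*Combined protocol and SAP*

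**What the plan says.** **Claims.** Section 2.1.1 sets out to evaluate whether the workshop "is effective in reducing the psychological distress experienced by parents and education staff who work with children with Intellectual Disability". The first hypothesis in 1.1 reads "The intervention will be effective in significantly reducing the psychological distress self-reported by parents and teachers who work with children with IDs". The other two hypotheses, three of the four quantitative research questions and two of the secondary objectives use the same language, for example "To evaluate whether the intervention is effective in reducing the self-reported burnout of education staff". The fourth research question differs and asks only about change: "Is there a significant change in the parents and education staff Acceptance and Commitment Therapy processes".

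**Design.** Sections 3 and 4.1 describe about 40 people in four workshop groups of ten. Section 6.1 gives three measurement times: before the first session, after the last, and about six weeks later. No control arm, waitlist or randomisation is described.

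**Analysis.** Section 2.2.1 names the DASS-21 as primary without choosing a score or a time point. Section 8.1 powers a within-between interaction for two groups and three measurements (f = 0.25, alpha 0.05, power 0.80) and arrives at 28 participants, with 12 of the 40 expected to be lost. Section 8.2 applies a repeated-measures ANOVA with that interaction to every dependent variable and adds that significant effects will be followed up. The two groups are not defined. Under 2.2.2 the burnout inventory is for education staff only.

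**The concern.** There are two linked problems.

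The first is attribution. With one measurement before the workshop and no comparator, the workshop's effect cannot be separated from the passage of time, regression to the mean, repeat testing or other care. The documents leave room for these: schools identify staff who might benefit, parents are identified from current clinical caseloads as well as through schools (5.1), and participants may wait for a group without being measured (3). The Background holds an earlier uncontrolled parent workshop to exactly this standard, saying that "the changes could not be reliably attributed to the intervention in the absence of appropriate controls". By contrast, the support-staff study that guided the effect size was one "with a randomised waitlist control design and six-week follow-up".

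The second is that no result is designated as the answer. The interaction that is named and powered does not, on its only evident reading, ask whether distress falls. At stake is the headline: a fall in DASS-21 from any cause could be reported as effectiveness, and a null interaction could be reported as its absence. The design supports neither conclusion.

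**Working it through.** **Step 1: reproduce the 28.** Inputs from 8.1: k = 2 groups, m = 3 times, f = 0.25, alpha = 0.05, power 0.80. The correlation between repeated measures (rho) is not stated, so I show 0.3, 0.5 and 0.7. Sphericity is assumed.

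For the interaction, lambda = f² × N × m / (1 − rho), with df1 = (k − 1)(m − 1) = 2 and df2 = (N − k)(m − 1) = 52 at N = 28. At rho = 0.5, lambda = 0.0625 × 28 × 3 / 0.5 = 10.5, which gives power 0.812. The smallest even N reaching 80% is 28, so the plan's figure reproduces at rho = 0.5. It would be 38 at rho = 0.3 and 18 at rho = 0.7.

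**Step 2: the time effect at the same f.** With two groups and three times, lambda and both degrees of freedom are the same as for the interaction. Power with 28 is therefore 66%, 81% and 96% at rho = 0.3, 0.5 and 0.7. The sample size carries over if the omnibus time effect becomes the primary test.

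**Step 3: what each term responds to.** Take the two groups as parents and staff, 14 each (assumed). A fall of size s, reached after the last session and held at six weeks, has f = s × √(2/9), so f = 0.25 corresponds to s = 0.25 / 0.471 = 0.53 SD. If both groups fall by 0.53 SD, the time test is significant in 66%, 81% and 96% of studies. The interaction stays at its 5% error rate by construction, because the groups do not differ in change.

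**Step 4: drift without a workshop effect (illustration).** Suppose scores fall by s for other reasons, equally in both groups. Then lambda = 28 × (2/3) × s² / (1 − rho). At rho = 0.5, s = 0.2 gives lambda = 1.49 and s = 0.4 gives 5.97.

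| Assumed drift | rho 0.3 | rho 0.5 | rho 0.7 |
|---|---|---|---|
| 0.2 SD | 13% | 17% | 26% |
| 0.3 SD | 25% | 34% | 53% |
| 0.4 SD | 42% | 56% | 79% |

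Entries are the chance of a significant time effect when the workshop does nothing. The documents give neither the drift nor rho.

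**Step 5: if one contrast were primary instead.** For before-to-six-weeks, lambda = N × s² / (2(1 − rho)). With s = 0.53 and N = 28, power is 63%, 77% and 94%. Reaching 80% needs 30 completers at rho = 0.5 and 42 at rho = 0.3. With 30% loss (12/40), that means recruiting 30 / 0.7 = 43 or 42 / 0.7 = 60, against the planned 40. The result depends on how f = 0.25 is translated: at rho = 0.5, a linear change (0.61 SD) gives 88% and a two-point change of 0.50 SD gives 72%.

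**Step 6: burnout.** Only staff complete it, so a parent-by-staff interaction does not exist. With an assumed 14 staff (df 2, 26), the time effect at f = 0.25 has 35%, 48% and 70% power. The 95% interval for a single change, t × √(2(1 − rho)/14), has half-width 0.68, 0.58 and 0.45 SD.

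**The case against.** **The plan would look at change.** Section 8.2 says that significant effects will be followed up, the ANOVA will produce a time effect, and means and SDs are reported. This stands in part. A reader might infer that the plan has no test of change, or that a null interaction would necessarily be declared a failure. The text supports neither. What remains is that nothing names the time effect as the answer to the objective.

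**The framework is not a binary one.** Section 3 says realist evaluation regards trials as "overly focused on aggregate outcomes which evaluate interventions in a binary way as successful or unsuccessful", and it plans qualitative corroboration. That tempers how results may be read, but it does not supply attribution or alter the wording of the objectives and hypotheses.

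**Two readings are inferred.** That the study is uncontrolled follows from the absence of any described comparator; the protocol does not use the word of itself. That the two groups are parents and staff is the only evident reading, but it is not stated. The burnout point and the 5% figure depend on it.

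**The sizes are assumed.** The drift, the correlations and the 14/14 split have no source in the documents. This is right, and the figures are illustrations. The logical point does not need them.

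**Conclusion.** The point holds. As worded, the primary objective, two secondary objectives, three research questions and all three hypotheses claim more than the design can show, and the term named and powered does not test whether distress falls. This needs correcting rather than merely clarifying, because following the plan as written leads to an effective or not-effective conclusion that the study cannot support.

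Its limits should be equally clear. A reader might infer that the sample size is wrong, but it is not: 28 reproduces at rho = 0.5 and serves the omnibus time effect equally well. A reader might also infer that a single-group study of this size is illegitimate or must have a control. The documents do not support that either; the design is acceptable if its claim is limited to change. The conclusion on attribution rests only on there being no described comparator and one pre-workshop measure. The conclusion on the interaction rests on the parents-versus-staff reading. The power figures rest on assumed correlations and sphericity.

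**What to change.** 1. **Claims (1.1, 2.1.1, 2.1.2).** Reword the affected objectives, questions and hypotheses to change in the outcome, as the fourth research question already does. Do not write an attendance restriction into the objective. State that any change cannot be attributed to the workshop alone.

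2. **Primary test (2.2.1, 8.1, 8.2).** Define the two groups. Name the time effect on the DASS-21 total score as the single primary test, and restate the sample-size basis for it, including the assumed correlation. The omnibus test has no direction, so report the before-to-post and before-to-six-week changes as follow-up estimates with direction and 95% confidence intervals. If one contrast is preferred as primary, use it in place of the omnibus test and restate the power in 8.1 (Step 5 of the working).

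3. **Interaction and burnout (8.2).** State that the interaction tests only whether the two defined groups differ in change. Analyse burnout by the time effect in staff alone, and report it mainly as an estimate with its interval.

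4. **Limitation.** Disclose that the exclusion in 5.2.1 of people who miss a session may restrict the result to those who attended every session.

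**Cost.** A weaker headline claim and, if a single contrast is chosen, a somewhat lower stated power for the same 0.53 SD step. With the omnibus time effect, no extra participants, visits or measurements are needed. A waitlist comparison or a measurement during the wait would support a stronger claim, but at greater cost.
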